10- One (1) lesional (L) and One (1) non-lesional (NL) biopsy will be collected at V2 (baseline), One (1) lesional (L) biopsy will be collected at V4 (Week 4) and at V7 (Week 16). One (1) optional lesional (L) will be collected at EoS (V10 for Responders or V11 for Non-Responders). Each skin biopsy of 4.5 mm punch (split into half for IHC and RNASeq) should be collected prior to trial drug infusion.

11- Photographs of skin lesions are to precede skin biopsies and study drug administration. Please refer to Section [5.6](#).

12- Skin tape stripping samples will be collected as close as possible to the site of the skin biopsy and at the same timepoint. Skin tape stripping samples must be taken before biopsies are taken and before trial drug infusion. One (1) L and one (1) NL at V2; one (1) L at V4 (Week 4) and V7 (Week 16); and one (1) optional lesional (L) at EoS(V10 for Responders or V11 for Non-Responders).

13- pre dose PK and ADA and Nab samples will be collected within 2 hour period prior to infusion. In addition, all biomarkers samples will be collected prior to trial drug infusion. Please refer to Section [5.3](#).

14- Microbiome samples must be taken before biopsies are taken and before trial drug infusion.

15- Deoxyribonucleic acid (DNA) banking sample is optional. Participating patients are required to give informed consent specifically for this banking. Blood sample will be collected in a PAX-gene Blood DNA tube at day 1 (Visit 2). If not possible at Visit 2, this sample may also be collected during a later visit. The DNA banking sample must be collected prior to infusion of the trial drug infusion.

16- At V7 (Week 16) all patients will be evaluated with the EASI score. Non-responders will be re-allocated to receive BI open label trial drug from V7 (Week 16) onward until V10 (Week 28). Responders will be re-assigned to no treatment from V7 (Week 16) onward until V10 (Week 28) but will be expected to come to all visits.

Proprietary confidential information © 2020 Boehringer Ingelheim International GmbH or one or more of its affiliated companies

17- All assessments must be done prior to trial drug infusion. The questionnaires completed by patients should be done first before the investigator assessments. Please refer to Section [6.2](#).

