3.1 OVERALL TRIAL DESIGN AND PLAN

This is a double-blind, placebo-controlled study assessing the safety, tolerability and efficacy of 600 mg BI 655130 compared to placebo given intravenously every 4 weeks in patients with moderate to severe atopic dermatitis. Safety and tolerability will be evaluated based on AE data collected and physical examination at every visit. At W16 patients will be evaluated for response to treatment by the change in EASI score compared to baseline. Patients who have responded, defined as having attained at least 75% reduction in EASI score compared to baseline will no longer receive treatment and will be followed at W 20, 24 and 28 to evaluate the sustainability of their response. If this patient reaches a 50% reduction in EASI score compared to baseline prior to the planned EOS at Week 28, they will immediately perform EOS and will be given the opportunity to receive treatment in an open label extension trial.

Patients who have not responded, defined as attained less than 75% reduction in EASI score compared to baseline will receive 600 mg BI 655130 at W16, 20, 24 and 28. Patients re-allocated to treatment, who reach EOS will be offered participation in the extension trial if they meet the eligibility criteria.

After re-allocation at Week 16, a patient will know what treatment they are on but will remain blinded to the treatment received until Week 16.

Figure 3.1.1 Trial design

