4.2.2 Emergency procedures

Infusion reactions including anaphylactic reaction

In case of infusion reactions including anaphylactic reaction emerging during or after infusion of trial medication, the investigator should consider in accordance with severity of the reaction and local standard of care to:

- Immediately interrupt the infusion
- Treat with systemic anti-histamines, i.v. steroids, and in case of a severe allergic reaction (eg, anaphylactic reaction) epinephrine

Also draw a plasma sample for IgE and ADA as detailed in the Lab Manual (Central laboratory). Consider also the evaluation of histamine, serum tryptase, and complement components.

In case of infusion reaction, based on patient's clinical course and medical judgment, the infusion may be re-initiated in case of mild or moderate infusion reactions (according to Rheumatology Common Toxicity Criteria (RCTC) V2) at lower speed with gradual increase to complete the infusion as detailed in the Instructions for Preparation and Handling of BI 655130 in the ISF. In any case, the total duration of infusion should not exceed 180 minutes (3 hours).

In case of potential systemic allergic reaction, blood samples for determination of serum tryptase will be collected 0.5 h, 2 h, 6 h, 24 h after onset of the event.

In case of suspected drug related anaphylactic reaction (Appendix [10.1.1](#)) the investigator should discontinue treatment permanently with BI 655130.

Severe infections (according to RCTC V2), serious infections, opportunistic or mycobacterium tuberculosis infections.

Treatment of the infection should be initiated promptly according to local standard of care. No further trial medication should be administered until the active infection has resolved. Treatment with BI 655130 may be restarted when the patient has recovered according to investigator's assessment.

Overall, the choice of Standard of Care treatment will be left at the discretion of the investigator. The sponsor will not provide/supply SoC treatment (s) to the sites.

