5.2.3 Safety laboratory parameters

For the assessment of laboratory parameters, blood and urine samples will be collected by the trial site at the time points indicated in the [Flow Chart](#).

The parameters that will be determined are listed in Table [5.2.3: 1](#). The laboratory tests will be performed at a central laboratory.

However, local labs may be used for dosing decisions at visits involving i.v. administration of BI 655130 or placebo. The lab tests listed in Table [5.2.3: 1](#) can be collected and assessed locally by the investigator prior to study drug infusion to allow for immediate subject management; however, split or concurrent samples will be drawn and sent to the central laboratory for analysis.

In case the criteria for hepatic injury are fulfilled, a number of additional measures will be performed (please see Section [5.2.5.2](#) and the Drug Induced Liver Injury (DILI) Checklist provided in the ISF and the electronic data capture (eDC) system). The amount of blood taken from the patient concerned will be increased due to this additional sampling.

Clinically relevant abnormal findings (e.g. anemia, hypoproteinemia, hypoalbuminemia, hypocalcemia etc.) will be reported as baseline conditions or AEs. A clinically relevant value may be either in- or outside the reference range. Clinically relevant abnormal laboratory test results must be confirmed using an unscheduled visit laboratory kit and should be repeated until normalization or stabilization or until an alternative explanation has been found. Abnormal laboratory values will also be graded for intensity by using RCTC Version 2.0 criteria [\[R13-3515\]](#).

Instructions regarding sample collection, sample handling/processing and sample shipping are included in the laboratory manual in ISF.

Proprietary confidential information © 2020 Boehringer Ingelheim International GmbH or one or more of its affiliated companies

Table 5.2.3: 1 Safety laboratory tests (Central lab Assessment)

Category	Test Name
Haematology	Haematocrit Haemoglobin Red blood cell count (RBC) White blood cell count (WBC) Platelet count
Automatic WBC differential (relative and absolute)	Neutrophils, eosinophils, basophils, monocytes, lymphocytes
Manual differential WBC (if automatic differential WBC is abnormal)	Neutrophils (stabs), eosinophils, basophils, monocytes, lymphocytes

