6. INVESTIGATIONAL PLAN

6.1 VISIT SCHEDULE

All patients are to adhere to the visit schedule specified in the [Flow Chart](#). Each visit date (with its window) is to be counted from Day 1 (V2).

All deviations from the planned visit schedule are to be documented. If any visit has to be rescheduled, subsequent visits should follow the original visit date schedule. Additional visits for the purpose of retesting of laboratory parameters or AE monitoring may be included as deemed necessary by the investigator.

For detailed description of the trial procedures, please refer to the [Flow Chart](#).

Details relating to study drug administration are provided in Section [4.1.4](#).

Study measurements and assessments are scheduled to occur ‘before’ trial medication administration at dosing visits and are to be performed and completed prior to the trial drug administration (including pre-dose on Day 1 for PK, ADA, Nab and biomarkers). For planned individual plasma concentration sampling times refer to the [Flow Chart](#). At non-dosing visits sampling should be done after other study procedures have concluded. Sampling times will be recorded and used for pharmacokinetic analysis.

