6. GENERAL ANALYSIS DEFINITIONS

6.1 TREATMENTS

For basic study information on the treatment to be administered, assignment to treatment, and selection of dose, cf. Section 4 of the CTP.

In the blinded treatment phase, all patients will receive either intravenous doses of 600mg of BI 655130 solution for infusion (at weeks 0, 4, 8, and 12), or Placebo.

At Week 16, all patients will be evaluated with the EASI Score. Non-responders (EASI < 75) will be re-allocated to receive BI open label trial drug from Week 16 through Week 28; they will be followed until Week 44. Responders (EASI >= 75) will be re-assigned to receive no further trial treatment but will be expected to come to all visits up to Week 28, when EOS visit is planned.

The following trial periods/phases are defined:

Table 6.1: Flow chart of trial period/phases

Trial phase	Description	Start (included)	End (excluded)
Screening phase	Screening	Date of informed consent	Date of start of first infusion of study drug (day 1).
Blinded Treatment phase	Randomised On-treatment period	Date of start of infusion of first study drug (Day 1)	Week 16 visit date + 1 day
Open label Treatment phase ¹	Re-allocation period (Either open label BI655130 or No treatment)	Week 16 visit date + 1 day	Date of EoS Participation visit + 1 day

Dates are defined individually per patient. If more than one date is associated with a specific visit, measurements associated with a specific date are assigned to a study analysis phase according to the rules specified in the table. An analysis phase will not extend beyond the start date of the following phase.

¹ Non-responders (i.e. EASI<75) at Week 16 will be re-allocated to BI655130 600mg IV open label and will continue in the trial until Week 44. Responders (EASI>=75) at Week 16 will be re-allocated to no treatment and will be observed until Week 28 or the day when they return to a 50% reduction in EASI score (EASI50) and start the treatment in the extension trial.

Patients who discontinue the treatment but will continue on trial visits will be included in analyses with the available data. For patients who discontinue trial prematurely only available data will be used in the analyses.

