For the final analysis of the trial to be performed once all patients have completed through the planned period, results will be summarized including the data from the reallocation period (Open-label Treatment phase). Results will be presented separately and in descriptive manner. The time windows for data presentation in this analysis are described in [Table 6.7: 1](#). In addition, analyses including the data from the double-blind period (initially used for the Primary Analysis) will be re-run after the final database lock.

To distinguish between assignment to trial periods/phases and AE assignments, please, refer to [Table 6.1:2](#).

Table 6.1: 2 AE assignment to analysis treatment groups

Randomised treatment	EASI75 response at Week 16	Open-label period	AE assignment to analysis treatment group
PLACEBO	Responder	No Treatment	AE that occurred between first randomised study drug intake and min[(EoS visit date), (last randomised study drug administration date + 112 days)] will be analysed under PLACEBO. AEs occurring later will be listed only.
PLACEBO	Non-Responder	BI 655130 Treatment	AE that occurred between first randomised study drug intake and Week 16 visit date (excluding) will be analysed under PLACEBO. AEs occurring later will be analysed under Open-label BI Treatment.
BI 655130	Responder	No Treatment	AE that occurred between first randomised study drug intake and min[(EoS visit date), (last randomised study drug administration date + 112 days)] will be analysed under BI 655130. AEs occurring later will be listed only.
BI 655130	Non-Responder	BI 655130 Treatment	AE that occurred between first randomised study drug intake and Week 16 visit date (excluding) will be analysed under BI 655130. AEs occurring later will be analysed under Open-label BI Treatment.

Treatment groups up to Week 16 will be labelled as follows:

- **"Speso 600 mg IV q4w"** (i.e., patients randomised to BI 655130 600 mg)
- **"Placebo"** (i.e., patients randomised to Placebo)
- **"Overall Total"** (across treatments: Placebo and BI 655130 600 mg), where appropriate.

Treatment groups for the efficacy analysis after week 16 will be labelled as follows:

- **"Open-label treatment: No Treatment"**
 - **"Placebo"** (i.e., patients randomised to Placebo in the double-blind treatment period and who did not receive an open-label BI 655130 treatment starting from Week 16 (V7))

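### SAP Table 6.1: 2 starts the open-label AE window for non-responders at the Week 16 visit rather than at the first open-label infusion, which misassigns AEs when that infusion is delayed or never given

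*SAP*

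**What the plan says.** SAP 6.1, Table 6.1: 2 has one row per combination of randomised arm and Week 16 EASI75 response. For placebo non-responders, "AE that occurred between first randomised study drug intake and Week 16 visit date (excluding) will be analysed under PLACEBO", and then "AEs occurring later will be analysed under Open-label BI Treatment". The row for non-responders randomised to BI 655130 uses the same boundary. Neither row mentions an open-label infusion. The two responder rows instead run to the earlier of the EoS visit and the last randomised dose plus 112 days; later AEs are only listed.

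Protocol 3.1 plans the first open-label dose for the same visit: non-responders "will receive 600 mg BI 655130 at W16, 20, 24 and 28". Protocol 6.1 says that scheduled assessments at dosing visits "are to be performed and completed prior to the trial drug administration". Under Protocol 5.2.3, clinically relevant abnormal laboratory findings "will be reported as baseline conditions or AEs".

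SAP 7.8.1 has a convention for AEs recorded without a start time: onset on the day of the first BI 655130 administration counts as on-treatment. Protocol 8.3.1 makes the AE onset date mandatory and mentions no onset time. Protocol 7.3.4 assigns AEs to the on-treatment period until 16 weeks after the last dose.

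**The concern.** The randomised AE window opens at a dose, but the open-label window opens at a visit. The two agree only if the first open-label infusion takes place on the V7 date, and the protocol allows for cases where it does not:

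- Section 4.2.2, for severe, serious, opportunistic or tuberculosis infections: "No further trial medication should be administered until the active infection has resolved".
- Section 4.1.4: a positive urine pregnancy test stops the infusion.
- Section 3.3.4.1: treatment may be interrupted temporarily, or discontinued while the patient stays in the trial.
- Flow Chart footnote 3: patients who discontinue before V7 are classed as non-responders.

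In these cases a placebo patient who has never received BI 655130 can have AEs tabulated under it, and the same AEs drop out of the placebo column. The tables at stake are those for drug-related AEs (a secondary endpoint), SAEs and AESIs, where counts are low. The clearest example is a placebo non-responder with a severe infection, itself an AESI, whose onset is on the V7 date and which leads to the infusion being withheld. Table 6.1: 2 counts it under open-label BI 655130.

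There is also a mismatch of column and population. SAP 6.1 defines the open-label safety column by assignment to open-label treatment at Week 16, whereas SAP 6.3 defines SAF-OL by study medication received after re-allocation. A patient assigned but never dosed is in the first and not in the second.

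**Working it through.** **1. Planned conduct.** Study day = 7 × week + 1. Week 12 is Day 85, Week 16 is Day 113, Week 28 is Day 197 and Week 44 is Day 309. For non-responders the randomised AE window is Days 1 to 112 and the open-label window starts on Day 113. The first open-label infusion is also planned for Day 113. No whole day is misassigned; only the part of Day 113 before the infusion is. A visit that is itself late does no harm, because SAP 6.1 defines dates per patient and the boundary moves with the visit.

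**2. What the date-only convention covers.**

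| Non-responder and AE | Table 6.1: 2 | SAP 7.8.1 convention |
|---|---|---|
| Ex-placebo, dosed at V7, AE dated V7 | Open-label | Open-label (first BI 655130 day): agrees |
| BI-randomised, dosed at V7, AE dated V7 | Open-label | Silent: first BI 655130 day was Day 1 |
| Ex-placebo, infusion after V7, AE dated V7 or during the delay | Open-label | Does not apply: no BI 655130 given yet |
| Ex-placebo, never dosed open-label, AE from V7 on | Open-label | Does not apply |

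**3. Delayed infusion.** If the infusion is given d days after V7, d calendar days without open-label exposure go to the open-label window. The planned window is Days 113 to 309, that is 309 − 113 + 1 = 197 days. The delays are assumed, not documented: d = 3 gives 3/197 = 1.5%, d = 7 gives 3.6%, d = 14 gives 7.1%, d = 28 gives 14.2%.

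**4. Infusion never given.** Protocol 7.3.4 keeps AEs on-treatment until the last dose plus 16 weeks. With the last randomised dose at V6, that is Day 85 + 112 = Day 197; at V5, Day 57 + 112 = Day 169; at V4, Day 29 + 112 = Day 141. Table 6.1: 2 stops at Day 112 in each case, so up to 197 − 112 = 85 days move to the open-label label.

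**5. Size, events.** The AE rate is assumed from the PPP trial in Protocol 1.2.3, where 85.7% of placebo patients had at least one AE. As a Poisson mean this is −ln(1 − 0.857) = 1.95 per patient. The documents do not give the period for that percentage, so take 112 to 196 days: 1.95/196 = 0.0099 to 1.95/112 = 0.0174 per patient-day. A 14-day delay moves 0.14 to 0.24 AEs per delayed patient. A never-dosed patient with 85 days at issue moves 0.84 to 1.48.

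**6. Size, patients, under planned conduct.** SAP 7.8.1 counts patients, not events, so a placebo patient leaves the any-AE row only if no earlier AE was recorded. Assume 13 of 15 placebo patients are non-responders and 10 to 30% of AEs are findings dated to a visit, spread over the five post-baseline visits to Week 16 (V3 to V7 in Table 6.7: 1).

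- Rate over 112 days: V7 events = 13 × 1.95 × (0.10 to 0.30)/5 = 0.51 to 1.52. P(no earlier AE) is about 0.14. Patients: 0.07 to 0.22.
- Rate over 196 days: the mean to Week 16 is 1.95 × 112/196 = 1.11. V7 events = 13 × 1.11 × (0.10 to 0.30)/5 = 0.29 to 0.87. P(no earlier AE) = exp(−1.11) = 0.33. Patients: 0.10 to 0.29.

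These counts treat every V7 finding as reclassifiable. Sparse rows lack the protection of an earlier AE: there one patient is 1/15 = 6.7 percentage points.

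**The case against.** The case for leaving the table alone is strong under planned conduct. Dose and visit share a date, AE onset is required by date only, and sending doubtful same-day events to the active drug is conservative and already the SAP's convention. That stands, and V7-dated AEs should mostly stay where they are.

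A reader might infer that Table 6.1: 2 contradicts Table 6.1: 1, which ends the blinded phase at "Week 16 visit date + 1 day" (excluded) and so keeps V7 measurements in it. The documents do not support that: SAP 6.1 says that AE assignment is separate from phase assignment and follows Table 6.1: 2. A V7 laboratory value and the AE derived from it can still fall under different treatments, but by a stated rule. Nor is the onset date of such an AE certain. Protocol 5.2.3 requires confirmation with an unscheduled kit and does not say which date counts.

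For non-responders randomised to BI 655130, the event keeps a BI 655130 label, so the loss is only from the randomised comparison. Safety is descriptive, and individual values are listed. SAP 7.8 adds an overall AE table and a table by system organ class and preferred term, limited to the period up to Week 16. These soften the effect.

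One may also argue that a never-dosed non-responder does not belong in a row whose open-label period is BI 655130 treatment. But then no row covers that patient. None of this answers the delayed infusion, where the written rule assigns unexposed time to the drug.

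**Conclusion.** The point holds for a first open-label infusion that is delayed or never given, and for pre-dose findings on the V7 day. In the first case the boundary in Table 6.1: 2 departs from the residual-effect rule in Protocol 7.3.4 and from the SAP's own responder rows. For never-dosed patients, the open-label column (assigned) also conflicts with SAF-OL (received).

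A reader might go further and conclude that AEs arising on placebo are routinely charged to BI 655130. The documents do not support that. As planned, the infusion falls on the visit date, and the date-only convention gives the same result for ex-placebo patients.

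The size is small: well under one placebo patient in the any-AE row on the assumptions above (PPP trial AE rate, 13 of 15 non-responders, 10 to 30% visit-dated AEs), but possibly one patient, or 6.7 points, in the drug-related or AESI rows. For placebo non-responders the shift is always from placebo to BI 655130. How often the V7 infusion would be delayed or missed is not given, so the total cannot be estimated from the documents.

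**What to change.** In the two non-responder rows of Table 6.1: 2:

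1. Replace the Week 16 visit date as the boundary with the date, and the time where collected, of the first open-label BI 655130 infusion.
2. If that infusion is delayed or not given, keep AEs under the randomised treatment up to the earliest of that infusion, the EoS visit and the last randomised dose plus 112 days.
3. Keep the same-day convention for V7-dated AEs, except those documented as found at a V7 pre-dose assessment, which stay with the randomised arm.
4. Define the open-label AE column by treatment received, so that it matches SAF-OL.

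The cost is a few lines of SAP text and one change to a derivation. Protocol 5.3.1 already has the date and exact time of drug administration recorded. The downside is a short check of V7-dated AEs, which needs some judgement because no AE onset time is required. Limiting the exception to documented pre-dose findings keeps that check small.

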7.3.4 Safety analyses

Adverse events will be coded using the Medical Dictionary for Drug Regulatory Activities (MedDRA). Standard BI summary tables and listings will be produced. All adverse events with an onset between start of treatment and end of the residual effect period (REP), a period of 16 weeks after the last dose of trial medication, will be assigned to the on-treatment period for evaluation.

All treated patients will be included in the safety analysis. In general, safety analyses will be descriptive in nature and will be based on BI standards. No hypothesis testing is planned.

Statistical analysis and reporting of adverse events will concentrate on treatment-emergent adverse events, i.e. all adverse events occurring between start of treatment and end of the REP. Adverse events that start before first drug intake and deteriorate under treatment will also be considered as 'treatment-emergent'.

[figure not shown]
Frequency, severity, and causal relationship of adverse events will be tabulated by system organ class and preferred term after coding according to the current version of the Medical Dictionary for Drug Regulatory Activities (MedDRA) at database lock.

[figure not shown]
Laboratory data will be analysed both quantitatively as well as qualitatively. The latter will be done via comparison of laboratory data to their reference ranges. Values outside the reference range as well as values defined as clinically relevant will be summarised. Treatment groups will be compared descriptively with regard to distribution parameters as well as with regard to frequency and percentage of patients with abnormal values or clinically relevant abnormal values.

Vital signs, physical examinations, or other safety-relevant data observed at screening, baseline, during the course of the trial and at the end-of-trial evaluation will be assessed with regard to possible changes compared to findings before start of treatment.

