6.7 BASELINE, TIME WINDOWS AND CALCULATED VISITS

Measurements reported with date and time and taken prior to start of administration of trial treatment will be considered pre-treatment values. Measurements reported with a date only (and no time) and taken on the day of first administration of trial treatment will also be considered pre-treatment values. These pre-treatment values will be assigned to visits according to the nominal visit number as recorded on the eCRF or as provided by the laboratory. For definitions used in Safety analyses, refer to [Section 7.8](#).

Baseline, unless otherwise specified, is defined as the last measurement collected prior to the start of administration of the trial treatment.

Measurements taken after start of administration of trial treatment will be considered either on- or off-treatment values based on the definition in [Section 6.1](#), and will be assigned to visits for statistical analysis, if applicable, as defined below.

Analysis of AE data, concomitant medication or non-drug therapies will not be based on visits. Therefore, no assignment to time windows will be necessary for such data.

For derivation of the last value on treatment, minimum value on treatment, and maximum value in the trial phase, all values from the relevant phase (whether or not collected in any time window; see [Table 6.1: 1](#) for definition of the trial periods/phases) will be considered; these will be derived for analysis of laboratory and vital signs data. For identification of potentially clinically significant abnormal laboratory values, all values (whether or not selected in any time window) before the date of EoS Participation visit will be considered.

A graphical analysis of the ALT and total bilirubin will be performed (so called eDISH plot) based on the available data obtained during the on-treatment period.

All other safety, efficacy and biomarker measurements will be assigned to visits based on extended time windows around the planned visit dates, defined relative to the day of first trial treatment (which is scheduled for Visit V2). These extended time windows are defined in [Table 6.7: 1](#).

Table 6.7: 1 Time windows for assignment of efficacy, safety lab, vital signs, and biomarker measurements to visits for statistical analysis of the double-blind treatment period

Visit number / name	Visit label	Planned day	Time window (Days)				
			Window (per CTP)	Start (per CTP)	End (per CTP)	Start (extended)	End (extended)

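### SAP Table 6.1: 2 omits the 16-week residual-effect limit from its two non-responder rows, so late AEs in patients who stop open-label drug early still count as open-label BI 655130 events

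*SAP*

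**What the plan says.** Protocol 7.3.4 assigns to the on-treatment period AEs with onset "between start of treatment and end of the residual effect period (REP), a period of 16 weeks after the last dose of trial medication", and uses the same span to define treatment-emergent.

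SAP Section 6.1 makes Table 6.1: 2 the governing place for AEs: "To distinguish between assignment to trial periods/phases and AE assignments, please, refer to" that table. Its four rows follow two rules:

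- **Responder rows (placebo and BI 655130).** AEs are analysed under the randomised treatment up to "min[(EoS visit date), (last randomised study drug administration date + 112 days" (the SAP then closes the brackets). After that, "AEs occurring later will be listed only".
- **Non-responder rows (placebo and BI 655130).** AEs before the Week 16 visit date are analysed under the randomised treatment. From that date, "AEs occurring later will be analysed under Open-label BI Treatment". No end date and no reference to the last dose follow.

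Table 6.1: 1 defines three phases: screening, blinded treatment and open-label treatment. The last ends at "Date of EoS Participation visit + 1 day", whatever the date of the last infusion. SAP 6.7 says that measurements after the start of treatment "will be considered either on- or off-treatment values based on the definition in" Section 6.1. SAP Section 4, on changes from the planned analysis, reads NA.

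**The concern.** One table applies the protocol's residual effect period to half of its rows and leaves it out of the other half. The SAP does not explain the difference or declare it as a departure from the protocol.

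The situation can arise. The Flow Chart footnotes and Protocol 6.2.3 ask that patients who stop drug early stay for all remaining visits if possible. Protocol 5.2.5.2 collects all AEs until the individual patient's end of trial. SAP 6.1 includes the available data of patients who stop treatment but continue visits. An AE that starts well after the residual effect period would then be tabulated as an open-label BI 655130 event. In a responder, an AE equally remote from the last dose would only be listed.

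Safety and tolerability are the stated main objective (Protocol 2.1.1), and drug-related AEs are a secondary endpoint. With about 45 patients in the trial, one or two misplaced patients can visibly shift a reported percentage.

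**Working it through.** **Inputs**

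- Residual effect period: 16 weeks after the last dose (Protocol 7.3.4), so 16 × 7 = 112 days.
- Open-label doses at V7, V8, V9 and V10, on Days 113, 141, 169 and 197 (Protocol 3.1, Flow Chart).
- Planned end for non-responders not entering the extension: safety phone call at Week 44, Day 309 (Flow Chart).
- Last blinded dose: V6, Day 85.

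**Step 1: reproduce the plan's own dates**

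- Non-responder with all four open-label doses: 197 + 112 = Day 309, and Week 44 is 44 × 7 + 1 = Day 309. This agrees with Flow Chart footnote 20, which places the end of the residual effect period at Week 44.
- Responder with all blinded doses: 85 + 112 = Day 197, which is V10, the responder's planned EoS.

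For patients who receive every dose, the 112-day limit and the planned end of follow-up coincide in both groups. The limit matters only when dosing stops early.

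**Step 2: early stop of open-label drug, follow-up to Day 309**

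Excess = 309 − (day of last dose + 112). Share = excess ÷ (309 − 113) = excess ÷ 196.

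| Last open-label dose | Day | Residual period ends | Excess AE time | Share of open-label window |
|---|---|---|---|---|
| V7 | 113 | 225 | 84 days | 43% |
| V8 | 141 | 253 | 56 days | 29% |
| V9 | 169 | 281 | 28 days | 14% |
| V10 | 197 | 309 | 0 days | 0% |

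**Step 3: bounds on these figures**

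- After all four doses, the ±3-day windows allow at most 312 − (194 + 112) = 6 days.
- If an early stopper has only the minimum follow-up, an EoS visit 16 weeks after the last treatment (Flow Chart footnote 18), the excess is 0.
- If the patient's trial ends at V11 on Day 228, the excess is 228 − 225 = 3 days for a last dose at V7 and 0 for a later one.

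**Step 4: does other SAP text supply the missing limit for AEs?**

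- Table 6.1: 1 ends the open-label phase by EoS, not by last dose.
- Table 6.7: 2 contains last dose + 16 weeks, but as a visit window. SAP 6.7 states that AE analysis is not visit-based.
- SAP 7.8.1 invokes treatment-emergent AEs without giving an end date.

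None of these closes the non-responder rows.

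**Step 5: off-treatment status**

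SAP 6.7 relies on Section 6.1 to separate on-treatment from off-treatment values. Table 6.1: 1 has no off-treatment phase, so the cross-reference has nothing to resolve to.

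**The case against.** The best defence is that the residual effect period already applies. SAP 7.8.1 bases AE analysis on treatment-emergent AEs, and the protocol defines those by the 16-week limit. The SAP says it follows Protocol Section 7 and declares no change. SAP 7.8 describes its additional tables to Week 16 as excluding the residual effect period, which suggests that the main tables include it. On this reading Table 6.1: 2 only allocates events to columns, and the ADS Plan, which is not among the documents, may hold the limit. This is fair evidence of what the authors intended. It does not override explicit row text that sends every later AE to the open-label group, in a table whose other rows do state the limit.

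Some stronger readings are tempting, and the documents do not support them:

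- *The window never ends.* It is bounded in practice, because AE collection stops at the patient's end of trial.
- *The SAP contradicts itself through Table 6.7: 2.* Those windows do not govern AEs, so there is no contradiction on this point.
- *Off-drug time is confounded because restricted therapy may then begin.* Protocol 4.2.3.1 bars the listed medications throughout participation and extends the bar to End of Study for non-responders short of a 50% EASI reduction. Standard of care for worsening disease (Protocol 4.2.1) is allowed both on and off drug.
- *A patient count can be borrowed from the palmoplantar pustulosis trial in Protocol 1.2.3.* Its AE-related stops (5.3% and 15.8% on active drug) come from another disease. They count drug stops, not patients followed beyond the residual effect period.
- *Laboratory summaries carry the same 84-day excess.* They do draw on the whole phase in Table 6.1: 1, but laboratory tests are scheduled only to V11, which may fall anywhere from Week 32 to Week 44. The excess is often far smaller.

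**Conclusion.** The point holds in a limited form. As written, the two non-responder rows depart from Protocol 7.3.4 without a declared change, and they treat post-drug time differently from the responder rows beside them.

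The excess is up to 84, 56 or 28 days of AE time for a last open-label dose at V7, V8 or V9. That assumes planned visit days and follow-up to Day 309, and shorter follow-up reduces it, to zero if the trial ends 16 weeks after the last dose. The documents give no open-label discontinuation rate, so the number of patients affected cannot be computed.

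The consequence is modest. Affected events fall in the open-label column, which pools patients from both randomised arms. The placebo-controlled comparison and the primary endpoint are untouched, safety is descriptive without hypothesis tests, and any error attributes too many late events to drug rather than too few. The missing off-treatment phase in Table 6.1: 1 is a separate small gap with the same cause.

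**What to change.** In both non-responder rows of Table 6.1: 2, analyse AEs under Open-label BI Treatment from the Week 16 visit date to the earlier of (a) the patient's end of trial and (b) last open-label dose + 112 days. List later AEs only, as in the responder rows.

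Define end of trial in (a) to include the End of Study Safety Phone Call where it applies. Do not use the V11 date alone, because V11 may take place from Week 32. For a patient dosed on Day 197 with V11 on Day 228, a cap at V11 would discard 309 − 228 = 81 days that are still within the residual effect period.

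In Table 6.1: 1, end the open-label phase consistently with this rule for patients given open-label drug, and add an off-treatment phase so that the reference in SAP 6.7 resolves. If the wider AE window is deliberate, declare and justify it in SAP Section 4 instead.

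The cost is two table cells, one added row with its matching phase end, and a small programming change. The downside is that a few late AEs may move from a table to a listing. None are lost.
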